3.2.5 Subgroup analyses for primary endpoint in Part A

To assess the homogeneity of the treatment effect across various subgroups, analyses will be performed on the primary endpoint in Part A across the following subgroups (categories with fewer than 10% participants will be combined with other categories; for factors with only two categories, no subgroup analysis will be performed if fewer than 10% participants in one category):

- MS clinical subtypes
 - RRMS, SPMS, PPMS
 - Pooled RMS (relapsing SPMS + RRMS), non-relapsing SPMS, PPMS
 - Pooled RMS (relapsing SPMS + RRMS), pooled PMS (non-relapsing SPMS + PPMS)
- Background DMT (with concomitant DMT, without concomitant DMT)
- Age at screening (<50, \geq 50 years)
- Sex (Male or Female)
- Baseline BMI (<median, \geq median), median value refers to the median baseline BMI among all randomized participants.
- Baseline EDSS score (<4, \geq 4)

The estimated geometric mean ratio in each treatment group (ie, SAR443820 versus placebo) and the relative reduction under treatment with SAR443820 compared to placebo will be provided (point estimates and 2-sided 90% confidence intervals [CI], respectively) for each subgroup separately, using the same method as specified in [Section 3.2.2.1](#) for the main analysis of the

primary endpoint in Part A. Forest plots of geometric mean ratio and corresponding 90% CIs comparing SAR443820 to placebo within each subgroup will be provided.

Treatment by subgroup interaction and its p-value will be derived from a MMRM with terms for treatment, MS clinical subtypes (RRMS, SPMS, or PPMS), visit (Weeks 12, 24, 36, 48), treatment-by-visit interaction, log-transformed baseline sNfL levels, log-transformed baseline sNfL levels-by-visit interaction, subgroup (if different than the aforementioned covariates), and subgroup-by-treatment interaction as covariates. If a quantitative subgroup by treatment interaction is detected with nominal p-value < 0.1 for any subgroup factor, a further investigation will be performed to evaluate possible qualitative interaction.

3.3 SECONDARY ENDPOINT(S) ANALYSIS

The secondary endpoints detailed in this section covers the secondary efficacy endpoints mentioned in Table 1 under [Section 1.2](#) for Part A and Part B.

Other secondary endpoints analyses are defined in [Section 3.6.2](#) (AE, SAE), [Section 3.6.1](#) (laboratory abnormalities) and [Section 3.7.1](#) (PK).

3.3.1 Definition of endpoint(s)

Time to onset of 12-week CDP is defined as the time from randomization to the onset of an increase in EDSS score (defined as an increase of ≥ 1.0 point from the baseline EDSS score when the baseline score is ≤ 5.5 or an increase of ≥ 0.5 points from the baseline EDSS score when the baseline score is > 5.5) confirmed after a 12-week interval.

- The initial onset increase from baseline EDSS score must be observed at a routine quarterly visit.
- All intermediate EDSS scores (EDSS scores obtained after onset of progression and before the confirmatory assessment), if any, must maintain at least the minimum increase.
- Confirmatory EDSS assessment must be obtained at least 12 weeks after onset and at a routine quarterly visit.

Note: 12-week confirmation must be ≥ 78 days after onset. Given that visits are scheduled every 12 weeks with a time window of ± 3 days for conducting EDSS assessment in Part A, the minimum per protocol allowed time between 2 EDSS assessments scheduled 12 weeks apart is 78 days (12 weeks=84 days minus a 3-day window for each of the 2 visits, ie, $84-6 = 78$).

Time to onset of 24-week CDP is defined similarly with time to onset of 12-week CDP. The only difference is that for time to onset of 24-week CDP, the increase in EDSS score has to be confirmed over 24 weeks. Accordingly, the minimum per protocol allowed time between confirmation and onset is 154 days (6 months=24 weeks=168 days minus a 7-day for each of the 2 visits, ie, $168-14 = 154$). Both the initial onset and the confirmation must be observed at scheduled visits, and all intermediate EDSS scores if any must maintain at least the minimum increase.

If a participant dies due to MS, it will be considered a confirmed disability progression regardless of the baseline EDSS or the change in EDSS. The time to onset will be calculated as (date of EDSS assessment at a tentative onset of the event – date of randomization + 1) or (date of death – date of randomization + 1) if a tentative onset date does not exist. Death for other reasons than MS will not be considered a disability progression and the participant's event time will be censored at the date of last EDSS assessment.

The 9-HPT is a brief, standardized, quantitative test of upper extremity function (lower bound: 10 sec; upper bound: 300 sec). Two consecutive trials with the dominant hand are immediately followed by two consecutive trials with the non-dominant hand. Let D_1 and D_2 be the time to complete the 9-HPT for the dominant hand for the two trials and let ND_1 and ND_2 be the time to complete the 9-HPT for the non-dominant hand for the two trials. The overall 9-HPT is calculated as:

$$9HPT = \frac{2}{\left(\frac{2}{D_1 + D_2}\right) + \left(\frac{2}{ND_1 + ND_2}\right)}$$

For a participant who could not complete the 9-HPT due to a “physical limitation”, the maximum time (300 sec) will be used. In case of missing data for other reason than inability to complete the test, missing data will be treated as follows:

- In case only 1 trial was done for a hand, the average of the two trials will be replaced by the time for the available trial.
- In case 9-HPT was assessed for only one hand, the overall 9-HPT will not be calculated and considered missing.

A higher value of overall 9-HPT is indicative of higher disability. In case of values below (above) the lower (upper) bound, the value will be set to the respective bound.

The T25-FW is a quantitative mobility and leg function performance test based on a timed 25-foot walk; time in seconds to walk 25 feet (lower bound: 2.2 sec; upper bound: 180 sec). For each assessment, 2 trials are performed. The score is the average of the times from the 2 trials (or single score if only 1 completed). For a participant who could not complete the 25-FW due to a “physical limitation”, the maximum time (180 sec) will be used. Missing values for other reasons will not be imputed. In case of values below (above) the lower (upper) bound, the value will be set to the respective bound. A higher value of T25-FW is indicative of higher disability.

Time to onset of 24-week CCDP, as assessed by composite endpoint EDSS-Plus (EDSS score, or T25-FW test, or 9-HPT), is to be confirmed over at least 24 weeks (3). Disability criteria for the individual components are defined as follows:

- Disability progression on the EDSS is defined as an increase of ≥ 1.0 point from the baseline EDSS score when the baseline score is ≤ 5.5 or an increase of ≥ 0.5 points from the baseline EDSS score when the baseline score is > 5.5 .
- Disability progression on the T25-FW test is defined as an increase (worsening) of $\geq 20\%$ from the baseline score.

- Disability progression on the 9-HPT is defined as an increase (worsening) of $\geq 20\%$ from the baseline score.

Change from baseline in EDSS-Plus refers to the following three different endpoints:

- Change from baseline in EDSS score
- Change from baseline in 9-HPT
- Change from baseline in T25-FW.

Analyses of the three endpoints will be conducted separately.

MSIS-29v2 evaluates the specific physical and psychological impact of MS from a participant's perspective (4). This patient reported outcome instrument has 2 subscales: 1) a physical impact score (20 items) and 2) a psychological impact score (9 items). The physical and psychological impact subscales of the MSIS-29v2 range from 0 to 100, with higher scores indicating greater physical or psychological impact. The physical impact score is computed by summing items number 1-20 inclusive. This score can then be transformed to a score on 0-100 scale using the formula below:

$$\frac{100 \times (\text{sum score} - 20)}{80 - 20}$$

The psychological impact score is computed by summing items number 21-29 inclusive. This score can then be transformed to a score on a 0 -100 scale using the formula below:

$$\frac{100 \times (\text{sum score} - 9)}{36 - 9}$$

For participants with missing data, but where at least 50% of the items in a domain have been completed (ie, a minimum of 10 items in the physical domain or 5 items in the psychological domain), then the missing item score will be imputed by the average score of the available items in the domain. For each domain, the sum score is computed as the sum of scores for all completed items and the imputed scores for the missing items and then transformed to a score on a 0-100 scale using the formulae mentioned above.

MSWS-12 measures the impact of walking impairment in participant with MS (5). This patient reported outcome instrument has 12 items with a global score ranging from 0 to 100. A higher score indicates better quality of life. The sum score of MSWS-12 is computed by summing all 12 items and then transformed to a score on a 0 – 100 scale using the formula below:

$$\frac{100 \times (\text{sum score} - 12)}{60 - 12}$$

Similarly to MSIS-29v2, for MSWS-12 measurements that are partially missing, if at least 50% of the items have been completed (a minimum of 6 items), the missing item score will be imputed by the average score of the available items. The sum score is computed as the sum of scores for all

completed items and the imputed scores for the missing items and then transformed to a score on a 0-100 scale using the formula mentioned above.

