8.1.9 MSWS-12

The multiple sclerosis walking scale (MSWS-12) measures the impact of walking impairment in patients with MS. This PRO instrument has 12 items with a global score ranging from 0 to 100. A higher score indicates better quality of life (30).

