
subpopulations of multiple sclerosis (MS)
 
 • To assess the effect of SAR443820 compared to placebo on biomarkers of neurodegeneration, inflammation, and disease progression • To assess efficacy of SAR443820 compared to placebo on patient-reported outcomes (PROs) assessing the physical and psychological impact of MS from the patient's perspective (MSIS-29v2) and the impact of MS on the individual's walking ability (MSWS-12) 	
 • Change from baseline compared to Week 48 in: plasma chitinase-3-like protein 1 (CHI3L1), serum glial fibrillary acidic protein (sGFAP), interleukin-1B (IL1B), IL6, IL8, TNFα, Chemokine (C-C motif) ligands 3 (CCL3), and Chemokine (C-C motif) ligands 4 (CCL4) • Change from baseline in MSIS-29v2 physical and psychological domains scoring at Week 12, 24, 36, and 48 • Change from baseline in MSWS-12 at Week 12, 24, 36, and 48

Part B

Objectives	Endpoints

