These time to event endpoints will be analyzed by a Cox proportional hazards model. The covariates included in the model are treatment group and MS clinical subtype (RRMS, SPMS, PPMS). The hazard ratio between treatment groups, its 95% confidence interval and the p-value will be estimated from this model with robust variance estimation (6). Comparison between treatment groups will also be assessed by a log-rank test stratified by MS clinical subtype (RRMS, SPMS, PPMS). Kaplan-Meier (KM) plots of the cumulative incidence rate will be provided by treatment group to depict the course of occurrence of event over time. The proportion of participants with events at given time points (eg, 12, 24, 36, 48, etc.) will be calculated using the KM estimates.

Continuous endpoints

Continuous endpoints include:

Part A

- Change from baseline in EDSS score at Week 48
- Change from baseline in 9-HPT at Week 48
- Change from baseline in T25-FW at Week 48
- Percent change from baseline in BVL at Week 48
- Change from baseline in the volume, number, and normalized T1 intensity of SELs at Weeks 12, 24, 36 and 48
- Change from baseline in the number of PRL at Weeks 12, 24, 36 and 48.

Part B

- Percent change from baseline in BVL at Week 96
- Change from baseline in the volume, number, and normalized T1 intensity of SELs to Week 96
- Change from baseline in the number of PRL at Week 96
- Change from baseline in EDSS at Week 96
- Change from baseline in 9-HPT at Week 96
- Change from baseline in T25-FW at Week 96
- Change from baseline in MSIS-29v2 physical and psychological domains score at Week 96
- Change from baseline in MSWS-12 at Week 96

Summary statistics including mean, standard deviation, median, interquartile range (Q1, Q3), minimum, and maximum will be provided for these continuous endpoints at scheduled visits. Only non-missing data will be included. For change/percent change from baseline, only participants with baseline and at least one post-baseline assessment will be summarized.

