Normalized T1 intensity of SELs may be explored using linear mixed model. The model will include the treatment group (SAR443820 or placebo), MS clinical subtype (RRMS, SPMS, or PPMS), time (from randomization to the date of MRI sample being collected), treatment-by-time interaction, baseline value of normalized T1 intensity of SELs as the fixed effects. Both intercept and the coefficient for time are assumed to have participant-level random effects and these two random effects are assumed to be independent.

The other continuous endpoints will be analyzed using a similar MMRM approach as described for the primary endpoint of Part A in [Section 3.2.2.1](#), except that the log-transformed baseline sNfL levels will be replaced by the baseline values of the corresponding endpoint. Appropriate transformation will be used if necessary (eg, log-transform). Plots of least squares means

(\pm standard error) over time will be provided. Plots of mean (\pm SE) and/or mean change (\pm SE) over time will also be provided.

No sensitivity or subgroup analyses will be conducted.

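### MSWS-12: the stated direction (higher is better) sits badly with an unreversed sum on an impact-of-impairment scale, and the item coding that would settle it is not printed

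*SAP*

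**What the plan says.** Protocol 8.1.9 states that the MSWS-12 "measures the impact of walking impairment in patients with MS", gives a global score from 0 to 100, and says that higher is better. It prints no scoring formula and no item coding.

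SAP 3.3.1 repeats the construct, the range and the direction: "A higher score indicates better quality of life". It alone adds the scoring. "The sum score of MSWS-12 is computed by summing all 12 items", and the sum is then rescaled as 100 × (sum − 12)/(60 − 12). No item is reversed, and the section does not say which end of the response scale is worse.

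The same section scores the two MSIS-29v2 subscales by plain sums with the same form of rescaling, and describes them "with higher scores indicating greater physical or psychological impact".

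The score is used in two places:
- Part A, tertiary (SAP 1.2, Table 1): "Change from baseline in MSWS-12 at Week 12, 24, 36, and 48".
- Part B, secondary (SAP 3.3.2): "Change from baseline in MSWS-12 at Week 96".

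**The concern.** A plain sum keeps whatever direction its items have. On a scale presented as the impact of an impairment, the natural reading is that a larger sum means more impact, which is worse. The direction sentence says the opposite, and nothing in either document explains why.

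Direction is part of an endpoint's definition. If the sentence is wrong and the outputs follow it, a rise in MSWS-12 would be described as improvement when walking has deteriorated, and a treatment difference would be credited to the wrong arm. A 2-sided p-value gives no warning of this, because it is the same whichever way the sign is read.

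**Working it through.** **Inputs, all from SAP 3.3.1.** MSWS-12: 12 items, minimum sum 12, maximum sum 60. MSIS-29v2 physical: 20 items, sums 20 to 80. MSIS-29v2 psychological: 9 items, sums 9 to 36. The implied MSWS-12 item range is 12/12 = 1 to 60/12 = 5.

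**Step 1: reproduce the stated range.** S = 100 × (sum − 12)/48.

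| Every item scored | Sum | S |
|---|---|---|
| 1 | 12 | 0 |
| 2 | 24 | 25 |
| 3 | 36 | 50 |
| 4 | 48 | 75 |
| 5 | 60 | 100 |

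The 0 to 100 range reproduces exactly, so the arithmetic is right. The score rises by 100/48 = 2.08 points for each one-level rise on one item. It is strictly increasing and contains no reflection.

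**Step 2: compare with MSIS-29v2.** Physical: 100 × (20 − 20)/60 = 0 and 100 × (80 − 20)/60 = 100. Psychological: 100 × (9 − 9)/27 = 0 and 100 × (36 − 9)/27 = 100. The form and orientation are the same as for MSWS-12.

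| | MSWS-12 | MSIS-29v2 |
|---|---|---|
| Construct | impact of walking impairment | physical and psychological impact of MS |
| Scoring | plain sum, rescaled upward | plain sum, rescaled upward |
| Stated direction | higher = better | higher = greater impact |

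**Step 3: try both possible item codings.** Take a one-level rise on all 12 items, sum 24 to 36. S goes from 25 to 50, a change of +25.

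- If a higher code means more limitation, the participant is worse by 25 points. The direction sentence calls this an improvement. Sentence and formula conflict.
- If a higher code means less limitation, the participant is better by 25 points. Sentence and formula agree, but the coding that makes them agree is not written down.

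**Step 4: what changes numerically.** The plan computes one score, S. A wrong label on S leaves every estimate, standard error, CI and p-value as it was. Only the words benefit and harm change places.

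**The case against.** The strongest reply is that the documents contain no outright contradiction. Protocol and SAP agree with each other on direction, and the formula is compatible with either item coding. The anchors belong to the questionnaire and the CRF, and both documents cite a source for the instrument that was not consulted here. The MSIS-29v2 comparison is suggestive only: it is a different instrument (80/20 = 4 as its highest item code, against 5 for MSWS-12), and its anchors are not printed either. All of this stands, and it is why the point is put conditionally. It does not remove the point. The agreement is one sentence appearing twice, and the Protocol gives no scoring that could support it.

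A reader might infer that the direction is proven wrong. The documents do not support that, because no passage says which end of an item is worse.

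A reader might also infer that orientation could alter the p-value, since SAP 3.3.2 and 3.4.2 allow that "Appropriate transformation will be used if necessary (eg, log-transform". That does not follow from the plan. No log transform is specified for MSWS-12, and the plan calculates only one orientation, so a mislabelled score gives the same results on any scale.

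The stakes are also modest. Protocol 9.2.4 treats tertiary endpoints as descriptive, and the secondary use is in an open-label extension.

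**Conclusion.** The point holds in conditional form and is minor. As written, the direction sentence does not fit an unreversed sum of an impact scale unless higher item codes mean less limitation, and neither document says that they do. The inference rests on the named construct and on the parallel with MSIS-29v2, not on printed item anchors.

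If the sentence is wrong, the sign of every MSWS-12 change and treatment difference would be misread, in Part A (tertiary) and Part B (secondary). The magnitude, CI width and 2-sided p-value are unaffected. No decision rule uses the score, and the primary sNfL endpoint and the sample size are untouched. If the sentence is right, the SAP is still incomplete, because a reader cannot confirm from it what a high score means.

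**What to change.** Check the MSWS-12 item coding against the CRF before database lock, then do one of the following.

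- **If higher codes mean more limitation:** keep the formula. Replace the direction sentence in SAP 3.3.1 with: *A higher score indicates a greater impact of MS on walking (worse).* Label tables and figures so that a negative change is improvement. Align Protocol 8.1.9 at the next amendment; the analysis need not wait for it.
- **If higher codes mean less limitation:** keep the sentence and the formula, and state the item coding beside the formula.

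The cost is one coding check, one SAP sentence and, in the first case, output labels. The model and the missing-item rule stay as they are.

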3.3.2 Main analytical approach

All secondary efficacy endpoints in Part A and Part B will be analyzed using the randomized and treated population. Participants who permanently discontinue the IMP or permanently modify the background DMT will be asked and encouraged to stay in the study for the remaining visits. In this case, all measurements collected after the treatment status change during the planned treatment periods will be included in the analysis.

Categorical endpoints with count data

Categorical endpoints with count data include:

Part A

- Average number of new gadolinium- (Gd-) enhancing T1-hyperintense lesions per scan from randomization to Week 48
- Annualized rate of new/enlarging T2-hyperintense lesions from randomization to Week 48
- Annualized relapse rate (ARR) of RMS population (relapsing SPMS and RRMS) from randomization to Week 48

Part B

- Number of new gadolinium- (Gd-) enhancing T1-hyperintense lesions from Week 48 to Week 96
- Annualized rate of new/enlarging T2-hyperintense lesions from Week 48 to Week 96
- ARR of RMS population (relapsing SPMS and RRMS) from randomization to Week 96

A negative binomial regression model with robust variance estimation will be used to analyze these categorical endpoints with count data. The robust variance can be estimated by specifying the participant identifier in the repeated statement using SAS PROC GENMOD (version 9.4 or later).

For analyzing the average number of new gadolinium- (Gd-) enhancing T1-hyperintense lesions per scan and annualized rate of new/enlarging T2-hyperintense lesions, the model will include the total count of the respective type of lesion across all scheduled MRI scans during the observation duration as the response variable, with treatment group, baseline lesions count and MS clinical subtype (RRMS, SPMS, or PPMS) as covariates. For Part B endpoints, the baseline lesions count will be replaced by the Week 48 lesions count. The offset variable will be the log transformed number of MRI scans during the observation duration for T1 lesions and log transformed observation duration for T2 lesions. The observation duration for Part A is from randomization to the last MRI scan on or prior to Week 48. The observation duration for Part B is from the end of Week 48 to last MRI scan on or prior to Week 96. The average number of lesions per scan (95% CI) for Gd-enhancing T1-hyperintense lesions and the annualized rate (95% CI) of new/enlarging T2-hyperintense lesions for each treatment group will be estimated from the model along with the relative risk (95% CI, p-value) for SAR443820 compared to placebo. The adjusted mean value

within treatment group is based on a sample size dependent weight within each categorical covariate (ie, weight by overall proportion of participants in each stratum or categorical factor, also called “population weight”).

For ARR of RMS population (relapsing SPMS and RRMS), a similar negative binomial regression model will be used. The model will include the total number of relapses per participant occurring in the planned treatment period as the response variable, with treatment group as the covariate. Log transformed observation duration from randomization to Week 48 for participants complete Part A, or from randomization to the last contact date for participants discontinued in Part A will be the offset variable for the ARR of RMS population in Part A. Log transformed duration from randomization to Week 96, except when a participant withdraws early from the study, in which case, the log transformed duration from randomization to the last contact of the participant before Week 96 will be the offset variable for the ARR of RMS population in Part B. The estimated ARR for each treatment group and corresponding 2-sided 95% CI will be derived from the negative binomial model where the adjusted mean value within treatment group is based on population weight. The relative reduction in ARR with SAR443820 compared to placebo, its 2-sided 95% CI and p-value will be provided.

Time-to-event endpoints

Time-to-event endpoints defined in Part A include:

- Time to onset of 12-week CDP from baseline as assessed by the EDSS score
- Time to onset of sustained 20% increase in 9-HPT confirmed over at least 12 weeks
- Time to onset of sustained 20% increase in T25-FW confirmed over at least 12 weeks

Time-to-event endpoint defined in Part B include:

- Time to onset of 24-week CDP from baseline as assessed by the EDSS score
- Time to onset of sustained 20% increase in 9-HPT confirmed over at least 24 weeks
- Time to onset of sustained 20% increase in T25-FW confirmed over at least 24 weeks
- Time to onset of CCDP, confirmed over at least 24 weeks (6-month CCDP), by the EDSS Plus composite (EDSS score increase, or 20% increase in the T25-FW test, or 20% increase in the 9-HPT)

These time to event endpoints will be analyzed by a Cox proportional hazards model. The covariates included in the model are treatment group and MS clinical subtype (RRMS, SPMS, PPMS). The hazard ratio between treatment groups, its 95% confidence interval and the p-value will be estimated from this model with robust variance estimation (6). Comparison between treatment groups will also be assessed by a log-rank test stratified by MS clinical subtype (RRMS, SPMS, PPMS). Kaplan-Meier (KM) plots of the cumulative incidence rate will be provided by treatment group to depict the course of occurrence of event over time. The proportion of participants with events at given time points (eg, 12, 24, 36, 48, etc.) will be calculated using the KM estimates.

Continuous endpoints

Continuous endpoints include:

Part A

- Change from baseline in EDSS score at Week 48
- Change from baseline in 9-HPT at Week 48
- Change from baseline in T25-FW at Week 48
- Percent change from baseline in BVL at Week 48
- Change from baseline in the volume, number, and normalized T1 intensity of SELs at Weeks 12, 24, 36 and 48
- Change from baseline in the number of PRL at Weeks 12, 24, 36 and 48.

Part B

- Percent change from baseline in BVL at Week 96
- Change from baseline in the volume, number, and normalized T1 intensity of SELs to Week 96
- Change from baseline in the number of PRL at Week 96
- Change from baseline in EDSS at Week 96
- Change from baseline in 9-HPT at Week 96
- Change from baseline in T25-FW at Week 96
- Change from baseline in MSIS-29v2 physical and psychological domains score at Week 96
- Change from baseline in MSWS-12 at Week 96

Summary statistics including mean, standard deviation, median, interquartile range (Q1, Q3), minimum, and maximum will be provided for these continuous endpoints at scheduled visits. Only non-missing data will be included. For change/percent change from baseline, only participants with baseline and at least one post-baseline assessment will be summarized.

Normalized T1 intensity of SELs may be explored using linear mixed model. The model will include the treatment group (SAR443820 or placebo), MS clinical subtype (RRMS, SPMS, or PPMS), time (from randomization to the date of MRI sample being collected), treatment-by-time interaction, baseline value of normalized T1 intensity of SELs as the fixed effects. Both intercept and the coefficient for time are assumed to have participant-level random effects and these two random effects are assumed to be independent.

The other continuous endpoints will be analyzed using a similar MMRM approach as described for the primary endpoint of Part A in [Section 3.2.2.1](#), except that the log-transformed baseline sNfL levels will be replaced by the baseline values of the corresponding endpoint. Appropriate transformation will be used if necessary (eg, log-transform). Plots of least squares means

(\pm standard error) over time will be provided. Plots of mean (\pm SE) and/or mean change (\pm SE) over time will also be provided.

No sensitivity or subgroup analyses will be conducted.

